6.2.2 Procedures for handling incorrectly enrolled or randomised participants

Participants who fail to meet the inclusion/exclusion criteria should not, under any circumstances, be enrolled or receive study medication. There can be no exceptions to this rule. Participants who are enrolled, but subsequently found not to meet all the eligibility criteria must not be randomised or initiated on treatment, and must be withdrawn from the study.

Where a participant does not meet all the eligibility criteria but is randomised in error, or incorrectly started on treatment, the Investigator should inform the AstraZeneca Study Physician immediately, and a discussion should occur between the AstraZeneca Study Physician and the Investigator regarding whether to continue or discontinue the participant from treatment. The AstraZeneca Study Physician must ensure all decisions are appropriately documented and that the potential benefit: risk profile remains positive for the participant.

6.2.3 Methods for assigning treatment arms

The actual treatment given to participants will be determined by the randomisation scheme in the IVRS/IWRS. The randomisation scheme will be produced by a computer software program that incorporates a standard procedure for generating randomisation numbers. One randomisation list will be produced for each of the randomisation strata. A blocked randomisation will be generated, and all centres will use the same list in order to minimise any imbalance in the number of participants assigned to each treatment arm.

Participants will be identified to the IVRS/IWRS per country regulations. Randomisation codes will be assigned strictly sequentially, within each stratum, as participants become eligible for randomisation. The IVRS/IWRS will provide the kit identification number to be allocated to the participant at the randomisation visit and subsequent treatment visits.

Participants will be randomised in a 2:1 ratio to either durvalumab (1500 mg q4w) or placebo. Participants will be stratified at randomisation based on the level of PD-L1 expression (PD-L1 <1% or PD-L1 \geq 1%) and prior therapy (cCRT or sCRT).
Every effort should be made to minimise the time between randomisation and starting study treatment. It is recommended that participants commence study treatment as soon as possible after randomisation (ie, on the same day after randomisation in the IVRS system).

The IVRS/IWRS may not be available after the final DCO for the study. In this case, a manual process will need to be followed.

6.2.4 Methods for ensuring blinding

The study will be conducted in a double-blind manner. The reconstituted durvalumab solution and its matching placebo will be identical in colour, and the iv bags used for administration will be identical with regards to size. All study treatment will be blinded using a translucent colored or opaque sleeve, after preparation by the unblinded pharmacist prior to dispensing to other study personnel, sleeve cover should be secured (e.g. using stapling, heat-sealing), to maintain double-blind conditions.

The IVRS/IWRS will provide to the pharmacists and/or other appropriate site staff the kit identification number to be allocated to the participant at the dispensing visit. Blinded and unblinded access and notifications will be controlled using the IVRS/IWRS. Investigators will remain blinded to each participant's assigned study treatment until the time of final analysis of the primary endpoint. To maintain this blind, a pharmacist and/or other appropriate site staff will be unblinded and responsible for the reconstitution and dispensation of all study treatment and will endeavour to ensure that there are no differences in time taken to dispense following randomisation. The unblinded pharmacist and/or other appropriate site staff will be wonitored by unblinded study monitors all of whom will have no further role in the management of study participants or data collection and will not have access to the study database. All other site personnel will be blinded for the dispensation of all study treatments.

In the event that the treatment allocation for a participant becomes known to the Investigator or other study staff involved in the management of participants, or needs to be known to treat an individual participant for an AE, the Sponsor must be notified promptly by the Investigator and if possible, before unblinding.

The IVRS/IWRS will be programmed with blind-breaking instructions. The treatment code should not be broken except in medical emergencies when the appropriate management of the participant requires knowledge of the treatment randomisation. Additionally, at the request of the Investigator, following discontinuation of IP and RECIST 1.1-defined progression of disease plus the additional regularly scheduled follow-up scan the participant can be unblinded. In the setting of rapid clinical progression, unblinding should be discussed with the AstraZeneca Global Study Physician and Study Statistician.

The Sponsor must be notified before the blind is broken unless identification of the study

treatment is required for a medical emergency in which the knowledge of the specific blinded study treatment will affect the immediate management of the participant's condition (eg, antidote available). In this case, the Sponsor must be notified within 24 hours after breaking the blind. The date and reason that the blind was broken must be recorded in the source documentation and eCRF, as applicable.

Study unblinding should not occur until database lock and all decisions on the evaluability of the data from each individual participant have been made and documented. AstraZeneca retains the right to break the code for SAEs that are unexpected and are suspected to be causally related to an IP and that potentially require expedited reporting to regulatory authorities.

The IDMC will be provided with unblinded data for their review, but AstraZeneca and designee staff and Investigators involved in the study will remain blinded.

6.3 Treatment compliance

Any change from the dosing schedule, dose delays/interruptions, and dose discontinuations should be recorded in the eCRF. Treatment compliance will be assured by study site reconciliation of medication dispensed.

The Investigational Product Storage Manager is responsible for managing the IP from receipt by the study site until the destruction or return of all unused IP. The Investigator(s) is responsible for ensuring that the participant has returned all unused IP.

The administration of all study treatments (including IPs) should be recorded in the appropriate sections of the eCRF. The Investigator or pharmacy must retain records of all study treatments administered. The Study Monitor will check these records to confirm the compliance with the protocol administration schedule.

Use of IP in doses in excess of that specified in the protocol is considered to be an overdose. Refer to Section 8.4.3 for procedures in case of overdose.

6.4 Concomitant therapy

The Investigator must be informed as soon as possible about any medication taken from the time of part II screening until the end of the clinical treatment phase of the study including the 90-day safety Follow-up Period following the last dose of study drug.

Any medication or vaccine including over-the-counter or prescription medicines, vitamins, and/or herbal supplements that the participant is receiving at the time of enrolment or receives during the study must be recorded along with:

• Reason for use

- Dates of administration including start and end dates
- Dosage information including dose, unit, and frequency

Participants must be instructed not to take any medications, including over-the-counter products, without first consulting with the Investigator.

Restricted, prohibited, and permitted concomitant medications are described in the following tables (Table 5 and Table 6). Refer also to the Dosing Modification and Toxicity Management Guidelines (see Section 8.4.5).

Prohibited medication/class of drug:	Usage:	
For all treatment arms		
Any investigational anticancer therapy other than those under investigation in this study	Should not be given concomitantly whilst the participant is on study treatment	
mAbs against CTLA-4, PD-1, or PD-L1 other than those under investigation in this study	Should not be given concomitantly whilst the participant is on study treatment	
Any concurrent chemotherapy, radiotherapy, immunotherapy, or biologic, or hormonal therapy for cancer treatment other than those under investigation in this study	Should not be given concomitantly whilst the participant is on study treatment. (Concurrent use of hormones for non-cancer-related conditions [eg, insulin for diabetes and hormone replacement therapy] is acceptable.	
Live attenuated vaccines	Should not be given through 30 days after the last dose of IP	
Immunosuppressive medications including, but not limited to, systemic corticosteroids at doses exceeding 10 mg/day of prednisone or equivalent, methotrexate, azathioprine, and tumour necrosis factor- α blockers	 Should not be given concomitantly, or used for premedication prior to the study treatment infusions. The following are allowed exceptions: Use of immunosuppressive medications for the 	
	 management of study treatment-related AEs Short-term premedication for participants receiving SoC CRT, in which the prescribing information or local guidance for the agent 	
	requires the use of steroids for documented hypersensitivity reactions, nausea/vomiting, or prophylaxis	
	• Use in participants with contrast allergies In addition, use of inhaled, topical, and intranasal corticosteroids is permitted. A temporary period of steroid treatment will be allowed if clinically indicated and considered to be essential for the management of non-immunotherapy-related events experienced by the participant (eg, chronic obstructive pulmonary disease, radiation, or nausea).	

Table 5 Prohibited concomitant medications

Prohibited medication/class of drug:	Usage:
EGFR TKIs	Should not be given concomitantly.
	Should be used with caution in the 90 days after the last dose of durvalumab.
	Increased incidences of pneumonitis (with third-generation EGFR TKIs) and increased incidence of transaminase increases (with first-generation EGFR TKIs) has been reported when durvalumab has been given concomitantly.
Herbal and natural remedies that may have immune-modulating and/or anticancer effects	Should not be given concomitantly unless agreed by the Sponsor

AE Adverse event; EGFR Epidermal growth factor receptor; mAb Monoclonal antibody; PD-1 Programmed death 1; PD-L1 Programmed death ligand 1; TKI Tyrosine kinase inhibitors.

Table 6Supportive medications

Supportive medication/class of drug:	Usage:
Concomitant medications or treatments (eg, acetaminophen or diphenhydramine) deemed necessary to provide adequate prophylactic or supportive care, except for those medications identified as "prohibited," as listed above	To be administered as prescribed by the Investigator
Best supportive care (including antibiotics, nutritional support, correction of metabolic disorders, optimal symptom control, and pain management	Should be used, when necessary, for all participants
Inactivated viruses, such as those in the influenza vaccine	Permitted

6.4.1 Other concomitant treatment

Medications other than those described above that are considered necessary for the participant's safety and well-being, may be given at the discretion of the Investigator and recorded in the appropriate sections of the eCRF.

6.4.2 Durvalumab drug-drug interactions

There is no information to date on drug-drug interactions with durvalumab either preclinically or in participants. As durvalumab is a monoclonal antibody and therefore a protein, it will be degraded to small peptides and amino acids and will be eliminated by renal and reticuloendothelial clearance. It is therefore not expected that durvalumab will induce or inhibit the major drug-metabolising cytochrome P450 pathways. As a result, there are no expected PK drug-drug interactions. The mechanism of action of durvalumab involves binding to PD-L1, and therefore, significant pharmacodynamic drug-drug interactions with the commonly administered concomitant medications are not expected. Despite this, appropriate clinical monitoring in all of the planned clinical studies will be conducted to evaluate any potential drug-drug interactions.

6.4.3 Rescue medication

As a result of immune-mediated adverse events (imAEs) that could potentially be experienced by participants on durvalumab, steroids and other immunosuppressant rescue medication has to be made available to this participant population. The 2 products that fall into the category of immunosuppressants are infliximab (eg, for colitis) and mycophenolate (eg, for hepatitis). AstraZeneca supply chain will only be responsible for sourcing these 2 rescue medications to the study sites if local regulations prevent the use of infliximab and mycophenolate in this indication, as they are considered off-label for management of immunotherapy-related toxicities. These rescue medications must be receipted, controlled, and administered by the unblinded pharmacist and/or other appropriate unblinded site staff and stored according to the labelled storage conditions, with temperature excursions reported accordingly by the unblinded pharmacist and/or other appropriate unblinded site staff. If required for use as a result of an imAE, then the IVRS/IWRS will provide to the unblinded pharmacists and/or other appropriate unblinded site staff the kit identification number to be allocated to the participant at the time, when the rescue medication is centrally supplied by AstraZeneca supply chain. Blinded and unblinded access and notifications will be controlled using the IVRS/IWRS.

6.5 Dose modification

Dose delays are permitted for immuno-oncology therapy (see Dosing Modification and Toxicity Management Guidelines in Section 8.4.5). However, **dose reduction is not permitted**.

6.6 Treatment after the end of the study

After the final DCO for this study, AstraZeneca will continue to supply open-label durvalumab monotherapy to participants who received durvalumab monotherapy until PD occurs as judged by the investigator. Tumour assessment scans will be performed in accordance with local clinical practice.

For participants continuing to receive durvalumab treatment following the final DCO and database closure, it is recommended that the participants continue the scheduled site visits and investigators monitor the participants' safety laboratory results prior to and periodically during treatment with durvalumab in order to manage AEs in accordance with the durvalumab Dosing Modification and Toxicity Management Guidelines (see Section 8.4.5).

In the event that a roll-over or safety extension study is available at the time of the final DCO and database closure, participants currently receiving treatment may be transitioned to such a study, and the current study would reach its end. The roll-over or extension study would ensure treatment continuation with visit assessments per its protocol, as applicable. Any participant who would be proposed to move to such a study would be given a new informed consent, as applicable.

Dependent on the analysis results of the study, a decision may be made to continue further data collection for a longer period with intent to analyse long-term OS and safety data to fulfil any other potential Health Authority requirements. Any additional long-term analysis may be further clarified through addendum to main statistical analysis plan, which will be developed before DCO for the long-term analysis.

7 DISCONTINUATION OF TREATMENT AND SUBJECT WITHDRAWAL

7.1 Discontinuation of study treatment

An individual participant will not receive any further IP (durvalumab or placebo) if any of the following occur in the participant in question:

- Withdrawal of consent from further treatment with IP. The participant is, at any time, free to discontinue treatment, without prejudice to further treatment. A participant who discontinues treatment is normally expected to continue to participate in the study (eg, for safety and survival follow up) unless they specifically withdraw their consent to all further participation in any study procedures and assessments (see Section 7.3).
- An AE that, in the opinion of the Investigator or AstraZeneca, contraindicates further dosing
- Any AE that meets criteria for discontinuation as defined in the Dosing Modification and Toxicity Management Guidelines (see Section 8.4.5)
- Pregnancy or intent to become pregnant
- Non-compliance with the study protocol that, in the opinion of the Investigator or AstraZeneca, warrants withdrawal from treatment with IP (eg, refusal to adhere to scheduled visits)
- Initiation of alternative anticancer therapy including another investigational agent
- Confirmed radiological progression (refer to Appendix E) or Clinical progression and Investigator determination that the participant is no longer benefiting from treatment with IP

Withdrawal of consent for biological sampling is included in Section 8.8.6.

7.1.1 **Procedures for discontinuation of study treatment**

Discontinuation of study treatment, for any reason, does not impact the participant's participation in the study. A participant who decides to discontinue IP will always be asked about the reason(s) for discontinuation and the presence of any AE. The participant should continue attending subsequent study visits, and data collection should continue according to the study protocol. If the participant does not agree to continue in-person study visits, a modified follow-up must be arranged to ensure the collection of endpoints and safety information. This follow-up could be a telephone contact with the participant, a contact with a relative or treating physician, or information from medical records. The approach taken should be recorded in the medical records. A participant who agrees to modified follow-up is not considered to have withdrawn consent or to have withdrawn from the study.

Participants who are permanently discontinued from further receipt of IP, regardless of the reason, will be identified as having permanently discontinued treatment. Participants who are permanently discontinued will enter Follow-up (see the SoAs).

Participants who permanently discontinue drug for reasons other than objective RECIST 1.1 disease progression should continue to have RECIST 1.1 scans performed every 8 weeks $(q8w) \pm 1$ week for the first 48 weeks (relative to the date of randomisation), and then every 12 weeks $(q12w) \pm 1$ week thereafter until RECIST 1.1-defined radiological PD plus an additional follow-up scan or death (whichever comes first) regardless of whether or not the participants started a subsequent anticancer therapy as defined in the SoAs.

If a participant is discontinued for RECIST 1.1-defined progression, then the participant should have 1 additional follow-up scan performed preferably at the next (and no later than the next) scheduled imaging visit, and no less than 4 weeks after the prior assessment of PD.

All participants will be followed for survival until the end of the study.

Participants who decline to return to the study site for evaluations should be contacted by telephone as indicated in the SoAs as an alternative.

Participants who have permanently discontinued from further receipt of IP will need to be discontinued from the IVRS/IWRS.

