- ^p Tumor assessment will be performed on images from CT (preferred) or MRI, each preferably with iv contrast, of the chest and abdomen (including the entire liver and both adrenal glands). Additional anatomy, e.g. pelvis, should be imaged based on signs and symptoms of individual participants at Baseline and follow-up. If a participant's scan is assessed as a RECIST 1.1-defined radiological progression, a follow-up scan for confirmation of the prior radiological progression is collected no earlier than 4 weeks after and no later than the next regularly scheduled imaging visit after the prior RECIST 1.1-defined PD, and this scan is evaluated using the confirmation of radiological progression criteria outlined in Appendix E. If the subsequent scan confirms the immediate prior radiological PD, no additional scans are required; however, if the subsequent scan does not confirm the immediate prior radiological PD, scanning should continue on the original imaging visit schedule until the next clinical progression/deterioration or RECIST 1.1-defined PD, which in turn will require a subsequent scan evaluated using confirmation of radiological progression criteria outlined in Appendix E. If an unscheduled assessment was performed and the participant has not progressed, every attempt should be made to perform the subsequent assessments at their next regularly scheduled visit. See Section 6.1.3 and Section 8.1 for additional details relevant to tumour assessment.
- Note: All assessments on treatment days are to be performed prior to infusion, unless otherwise indicated.

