Table 2Schedule of activities for participants who have discontinued treatment with durvalumab /placebo

	Time since last dose of IP								
	Day (±3)	±3) Months (±1 week)						12 months	
Evaluation	30	2	3	4	6	8	10	then every 2 months (±2 weeks) ^a	For details, see Section
CCI									8.5
Tumour assessment (CT or MRI) (RECIST 1.1) ^j	On-study tumour assessments occur $q8w \pm 1$ week for the first 48 weeks (relative to the date of randomisation) and then $q12w \pm 1$ week thereafter until RECIST 1.1-defined radiological progression plus 1 or more additional follow-up scans for confirmation of progression until confirmed radiological progression, the end of study, death, study discontinuation, or Sponsor decision (whichever comes first). The on-study schedule of $q8w \pm 1$ week (relative to the date of randomisation) for the first 48 weeks and then $q12w \pm 1$ week thereafter MUST be followed regardless of any delays in dosing. Additional scans to be completed per standard practice post-progression.							8.1	

Participants on Survival Follow-up at the time of final DCO for the study will be considered to have completed the study and will continue to receive treatment per local standard of care.

- ^b Will be administered using a site-based electronic device. It is preferred that PRO questionnaires are completed prior to any other study procedures and before discussion of disease progression to avoid biasing the participant's responses to the questions.
- ^c For women of childbearing potential only. A urine or serum pregnancy test is acceptable.
- ^d WHO/ECOG performance status should also be collected at other study site visits that the participant attends, if appropriate study site staff are available to collect such information. In addition, WHO/ECOG performance status should be provided when information on subsequent anticancer therapy is provided, where possible.
- e Details of any treatment for NSCLC (including surgery) after the last dose of IP must be recorded in the eCRF. At minimum, collect the start date and description of the subsequent anticancer therapy.

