During the Treatment Period, participants who are clinically stable at an initial Response Evaluation Criteria in Solid Tumors 1.1-defined radiological progression of disease may continue to receive study treatment at the discretion of the Investigator and participants. A follow-up scan is to be collected after the initial Response Evaluation Criteria in Solid Tumors 1.1-defined radiological progression of disease, no less than 4 weeks after the prior assessment of progression of disease and no later than the next regularly scheduled imaging visit, and this scan is evaluated using the Confirmation of Radiological Progression criteria outlined in Appendix E. Participants with confirmed PD who continue to receive study treatment at the discretion of the Investigator and participant (following consultation with AstraZeneca) can receive treatment until no longer having clinical benefit, and tumor
assessments should continue on their regular imaging schedule for the duration of treatment. If the subsequent scan does not confirm the immediate prior radiological progressive disease, scanning should continue until the next Response Evaluation Criteria in Solid Tumors 1.1defined radiological progression of disease, which in turn will require a subsequent scan evaluated using the Confirmation of Radiological Progression criteria outlined in Appendix E.

Follow-up of participants post discontinuation of study treatment

Participants who have discontinued study treatment due to toxicity or symptomatic deterioration, clinical progression, or who have commenced subsequent anticancer therapy will be followed up with tumour assessments until Response Evaluation Criteria in Solid Tumors 1.1-defined radiological progression of disease plus an additional follow-up scan or until death (whichever comes first) and followed for survival. PRO questionnaires will be followed up until PFS2.

Survival

All participants randomised in the study should be followed up for survival.

Independent Data Monitoring Committee:

The Independent Data Monitoring Committee will meet periodically in accordance with the IDMC charter to review safety assessments and make recommendations to continue, amend, or stop the study based on safety findings.

Full details of the Independent Data Monitoring Committee procedures and processes can be found in the Independent Data Monitoring Committee Charter.

Statistical methods

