A follow-up scan is to be collected after the initial RECIST 1.1-defined radiological PD, no less than 4 weeks after the prior assessment of PD and no later than the next regularly scheduled imaging visit and; this follow-up scan is evaluated using the Confirmation of Radiological Progression criteria outlined in Appendix E. If the subsequent scan confirms the immediate prior radiological PD, no additional scans are required; however, if the subsequent scan does not confirm the immediate prior radiological PD, scanning should continue until the next RECIST 1.1-defined radiological PD, which in turn will require a subsequent scan evaluated using the Confirmation of Radiological PD, which in turn will require a subsequent scan

If a participant has initial progression but changes to another anticancer treatment before that progression is confirmed, the follow-up scan should still be acquired on the regular imaging schedule.

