3.2.1 Progression-Free Survival (PFS)

The primary endpoint is PFS per RECIST 1.1 as assessed by BICR. PFS will be defined as the time from the date of randomisation until the date of objective disease progression or death (by any cause in the absence of progression) regardless of whether the patient withdraws from therapy or receives another anti-cancer therapy prior to progression (i.e., date of event or censoring – date of randomisation + 1).

Patients who have not progressed or died at the time of analysis will be censored at the time of the latest date of assessment from their last evaluable RECIST 1.1 assessment. However, if the patient progresses or dies after 2 or more missed visits, the patient will be censored at the time of the latest evaluable RECIST 1.1 assessment prior to the 2 missed visits (note: NE visit is not considered a missed visit). If the patient has no evaluable visits or does not have baseline data or have baseline data but no-post baseline data, they will be censored at study day 1 unless they die within 2 visits of baseline (16 weeks plus 1 week allowing for a late assessment within the visit window), which then will be treated as an event with date of death as the event date.

Given the scheduled visit assessment scheme (i.e. after randomisation every 8 weeks \pm 1 week for the first 48 weeks and then every 12 weeks \pm 1 week thereafter until clinical progression/deterioration) the definition of 2 missed visits will change over time, as described in [Table 6](#).

Table 6 PFS: Definition of 2 Missed Visits

Timing of Previous RECIST Assessment	Two Missed Visits	Explanation
Study day < 50 (before week 8 day 1)	17 weeks	17 weeks since the date of randomisation (if no post-baseline assessment) or 17 weeks since the previous RECIST assessment (if has post-baseline assessment) (i.e., 2 \times 8 weeks + 1 week for a late assessment = 17 weeks)
Study day 50 to < 274 (i.e., week 8 to week 39)	18 weeks	18 weeks since the previous RECIST assessment (i.e., 2 \times 8 weeks + 1 week for an early assessment + 1 week for a late assessment = 18 weeks)
Study day 274 to < 330 (week 40 to week 47)	22 weeks	22 weeks since the previous RECIST assessment

Timing of Previous RECIST Assessment	Two Missed Visits	Explanation

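### After study treatment stops, Protocol 7.1.1 and the Synopsis end imaging at PD plus one scan and do not cover a scan that fails to confirm PD; Table 2, Section 8.1 and SAP 3.1 require imaging to continue

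*Protocol*

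**What the plan says.** Five places govern when imaging ends once study treatment has stopped.

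- **Protocol 7.1.1, stopped for a reason other than RECIST progression:** scans continue "until RECIST 1.1-defined radiological PD plus an additional follow-up scan or death (whichever comes first"). The sentence goes on to cover subsequent anticancer therapy and closes with a pointer to the schedule of activities.
- **Protocol 7.1.1, stopped for RECIST progression:** "then the participant should have 1 additional follow-up scan performed preferably at the next (and no later than the next) scheduled imaging visit". This paragraph has no pointer to the schedule and does not mention a scan that fails to confirm.
- **Synopsis, follow-up after discontinuation:** imaging runs to RECIST progression "plus an additional follow-up scan or until death (whichever comes first) and followed for survival".
- **Table 2 (off-treatment schedule):** imaging runs to RECIST progression "plus 1 or more additional follow-up scans for confirmation of progression until confirmed radiological progression, the end of study, death", with study discontinuation and a Sponsor decision as further stops.
- **Protocol 8.1, repeated in SAP 3.1:** if the follow-up scan does not confirm, "scanning should continue until the next RECIST 1.1-defined radiological PD", and that progression needs a follow-up scan of its own.

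The primary endpoint is PFS by blinded independent central review (BICR). Under Protocol 8.1.1, BICR results are not given to Investigators. Under Protocol 9.4.1.2 and SAP 3.2.1, a participant with neither BICR progression nor death is censored at the last evaluable assessment.

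**The concern.** The Investigator's reading decides when imaging ends, but the BICR reading decides whether there is an event. A site cannot know that a BICR event is still missing. If imaging ends on an Investigator progression that the next scan did not confirm, a participant who could still have been followed is censored, and the cause is a judgement about disease status. That is potentially informative censoring in the primary endpoint. Sites that follow different sections would also give different follow-up.

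The situation is foreseeable. Protocol 4.2.3 warns that assessment after radiation may be difficult and may have to be repeated, and that response to immunotherapy can follow conventional progression. Treatment beyond a first progression is discretionary (Protocol 6.1.3), so participants can stop treatment on an unconfirmed one. Protocol 6.1.3 and 6.2.4 also allow unblinding on request once treatment has stopped and the follow-up scan has been done, without requiring confirmation. Later imaging decisions could then be made with the arm known.

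**Working it through.** **1. Where the texts part.** Take a participant off treatment with Investigator RECIST progression and one follow-up scan.

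| Follow-up scan | 7.1.1 and Synopsis | Table 2, 8.1, SAP 3.1 |
|---|---|---|
| Confirms | Imaging ends | Imaging ends |
| Does not confirm | Not addressed; read literally, imaging ends | Imaging continues |

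The conflict is confined to the second row.

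**2. What follows for BICR PFS if imaging ends there.**
- BICR called progression on the same scans: event.
- No BICR progression, death before two visits count as missed: event at death.
- Otherwise: censored at the last evaluable scan.

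The windows in SAP Table 6 reproduce:
- previous assessment before study day 50: 2×8 + 1 = 17 weeks
- day 50 to before day 274: 2×8 + 1 + 1 = 18 weeks
- day 274 to before day 330: 8 + 12 + 1 + 1 = 22 weeks
- day 330 onwards: 2×12 + 1 + 1 = 26 weeks

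**3. Example (assumed visits exactly on schedule, all scans evaluable).** Investigator progression at week 24, not confirmed at week 32, no BICR progression. Week 32 is study day 32×7 + 1 = 225, so the 18-week window applies and runs to week 32 + 18 = 50. Under 7.1.1 read alone, imaging ends at week 32. A death at week 45 is an event; a death at week 60 is censored at week 32. Under Table 2 and 8.1, scans at weeks 40 and 48 are still due, and a BICR progression at either would be an event. Under 7.1.1 alone it is never seen.

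**4. Size.** The planned PFS events, hazard ratio, maturity and power are redacted, so there is no stated figure to reproduce. As a scale only, assume 60% to 80% maturity in the 375 mITT participants (225 to 300 events), hazard ratios of 0.60 to 0.75, 2:1 allocation and two-sided 5%:

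power = Φ(|ln HR| × √(d × 2/3 × 1/3) − 1.96)

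For d = 225 and HR 0.70: 0.3567 × √50 = 2.522, less 1.96 = 0.562, power 0.713. With 10% of events lost, d = 202.5: 0.3567 × √45 = 2.393, less 1.96 = 0.433, power 0.667, a fall of 4.6 points.

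| BICR events lost (assumed) | Fall in power over the range (percentage points) |
|---|---|
| 2% | 0.1 to 0.9 |
| 5% | 0.4 to 2.2 |
| 10% | 0.9 to 4.6 |

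Nothing in the documents supports any of these loss rates. The fall also applies only if the follow-up-time trigger for the final PFS analysis comes first. If the event-count trigger comes first, lost events delay the cut-off instead.

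**The case against.** The strongest reply is that there is no real second rule. Section 7.1.1 does not tell sites to stop after a non-confirming scan; it is silent. Its first paragraph points to the schedule of activities, Protocol Section 8 makes adherence to that schedule mandatory, and every text that addresses the non-confirming scan says to continue. Harm also needs a chain of conditions: treatment stopped, Investigator progression not confirmed, a site that overlooks Table 2 and 8.1, no BICR progression on the same scans, and no death within the window.

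Most of this stands, and it limits the point to a narrow group. It does not remove it. The pointer in 7.1.1 follows the clause on subsequent therapy, so what it qualifies is unclear. The second paragraph of 7.1.1 and the Synopsis follow-up text have no pointer at all.

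SAP 4.2.1 mitigates in part. Investigator-assessed PFS, BICR/Investigator disagreement by arm and a count of premature censoring are all planned. An attrition analysis restores events after two missed assessments. None of these can recover scans that were never taken. The summary of Investigator-only progressions, which the SAP itself links to informative censoring, runs only if there is an important discrepancy, a term it does not define.

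Two stronger readings are tempting, and the documents do not support them.

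- **A reader might infer a third stopping rule, clinical progression.** Table 1 footnote p says "scanning should continue on the original imaging visit schedule until the next clinical progression/deterioration or RECIST 1.1-defined PD", but it then requires a further scan evaluated for confirmation, so that event triggers imaging and does not end it. SAP 3.2.1 has "thereafter until clinical progression/deterioration", but only in a parenthesis introducing the missed-visit table. SAP 3.1.1.2 and the Synopsis keep participants on imaging past symptomatic deterioration.
- **A reader might infer a hazard ratio shifted towards durvalumab.** That needs unequal rates of unconfirmed progression between arms, and false calls whose timing is tied to the participant's own later progression. If the timing is unrelated, the censoring is not informative. The documents give neither the rates nor the timing.

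**Conclusion.** The inconsistency is real and sits in current operative text. A site following 7.1.1 or the Synopsis alone may end imaging after an unconfirmed Investigator progression, and the participant can then be censored in the primary analysis although follow-up was still possible.

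The effect is limited to off-treatment participants with unconfirmed progression, no BICR progression, and no death within the 17- to 26-week windows. Its size and direction cannot be derived from the documents. Avoidable, possibly informative censoring matters more here than lost power.

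Two limits apply. Appendix E, which holds the confirmation criteria, was not in the text available to me. Reconciling the wording also leaves a separate route open: an Investigator progression that is confirmed but never called by BICR still ends imaging under every version of the rule.

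**What to change.** 1. Reconcile both paragraphs of Protocol 7.1.1 and the Synopsis follow-up text with Table 2, Protocol 8.1 and SAP 3.1, to which 7.1.1 already points, so that the non-confirming scan is treated the same everywhere. A cross-reference to 8.1 in each place would do.
2. As a wording clean-up, align the description of the assessment schedule in SAP 3.2.1 with SAP 3.1.
3. Add to SAP 4.2.1 an unconditional count, by arm, of participants whose imaging ended after an unconfirmed Investigator progression without BICR progression. It is informative even if the wording change comes too late for some participants.

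The cost is a protocol amendment or site clarification letter, a SAP edit and one table. It adds no imaging beyond what Table 2 already requires.
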